Patients who are diagnosed with PCa will be given the Memorial Anxiety Scale for Prostate Cancer (MAX-PC) which is a highly internally consistent, and concurrently and discriminately valid questionnaire used to identify levels of anxiety related to prostate cancer^{6,7} as well as the Generalized Anxiety Disorder-7 (GAD-7) scale, which is a valid, reliable, and efficient 7 item scale used to identify patients with generalized anxiety disorder and has also been effectively used in a population of men with prostate cancer^{8,9}.

Those PCa patients who have elected AS, obtain a score of ≥ 16 on the MAX-PC, and who meet other inclusion criteria, will be randomly assigned to the treatment or control group. Patients assigned to the treatment group will receive 12 weekly 1-hour sessions of structured group therapy intervention led by a licensed psychologist, in addition to AS educational material. Patients assigned to the control group will receive the standard AS educational material only. The research coordinator, who will be responsible for disseminating the educational material and answering patient questions regarding AS, will be blinded to the randomization outcome the the study subjects.

Patients in both the treatment group and control group will be monitored using MAX-PC, GAD-7, and Functional Assessment of Cancer Therapy-Prostate (FACT-P) questionnaires at various time points, as described below. We hypothesize that those patients who undergo group therapy will have a significant reduction in their disease-related anxiety, as reflected by a reduction in their MAX-PC score by the end of their 12-week group therapy intervention. Furthermore, we expect to see an improvement in their quality of life, as measured by the scores obtained on the FACT-P. In addition, results of the program intervention will be correlated with PSA level changes.

Interventions

- 12 1-hour group therapy sessions, occurring once a week
- Facilitated by licensed psychologist
- Group therapy will be conducted using a manualized CBT treatment for anxiety, modified to focus on disease-related anxiety, and incorporating mindfulness-based stress reduction exercises.
- Participants will complete the MAX-PC, GAD, and FACT-P during the 4th and 12th weeks of therapy. Those who are absent during the 4th week and/or 12th week will be given the questionnaires to fill out during the next session or within 7 days.

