2. Gender of Subjects: All subjects to be included in this study will be male.
3. Age of Subjects: The subjects of this study will be over the age of 40.
4. Racial and Ethnic Origin: No discrimination will be made based on race or ethnic origin of subjects.

5. Inclusion Criteria: Inclusion requirements for this study are men above the age of 40 with a primary diagnosis of Prostate Cancer, and initial MAX-PC score of ≥ 16 . In order to participate, patients must sign a consent form allowing related information to be included in this research. This form will be written in simple terms clearly stating the voluntary nature of their participation.
6. Exclusion Criteria: Subjects will be excluded from the study if prostate cancer is not their primary diagnosis. Subjects who, in the judgment of the investigator, cannot appropriately fill out the questionnaires will also be excluded from the study. Subjects will be excluded if they have pre-existing diagnosed psychiatric conditions, are currently taking psychotropic medications (e.g., antidepressants, anxiolytics, mood stabilizers), or have been diagnosed with cancer other than prostate cancer (and non-melanoma skin cancer), and/or evidence of active substance abuse. Participants in the treatment group who are absent from more than 3 therapy sessions will be excluded.
7. Vulnerable Subjects: Elderly subjects being treated for prostate cancer may have diminished decisional capacity. Subjects deemed in the judgment of the investigator to be unable to sign consent will be excluded from the study.

VI RISKS AND BENEFITS

1. The risks to the patient are:
 - a. The potential for unforeseen exposure of information and breach of confidentiality.
 - b. The possibility that a patient may feel uncomfortable answering certain questions regarding sexual and urinary function.
2. Protection against Risks.
 - a. In order to protect private patient information and confidentiality, the data will be password protected and encrypted.
 - b. If a subject feels uncomfortable with answering questions, they will be allowed to opt out of responding to those questions.
3. Potential Benefits to the Subjects. Potential benefits include patient treatment for anxiety and therefore possible quality of life improvement.

VII STATISTICAL ANALYSIS

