Statistical methods: The investigators will perform all data analysis. Two groups, the experimental (recipients of group therapy) and the control (literature only) will be compared for anxiety based on their MAX-PC and FACT-P questionnaire scores. PSA anxiety scores will be summarized via descriptive statistics (mean, median, standard deviation, range) at baseline, 4 weeks, and 12 weeks for each treatment arm. Average pre/post changes (12 weeks – baseline) will also be computed for each treatment arm, along with 95% confidence intervals. Analysis of covariance will be used to examine our primary hypothesis that 12-week anxiety scores will be lower in patients receiving group therapy by regressing 12-week PSA anxiety scores onto baseline PSA scores and an indicator variable for treatment arm (12 weeks of group therapy vs.

standard follow-up). The estimate, 95% confidence interval and statistical significance of the treatment effect are the main statistics of interest. In secondary analysis, a mixed effects model will be used when the outcome vector consists of all three measurements (baseline, 4 and 12 weeks) and via statistical contrasts will examine whether the relationship between PSA anxiety scores and time is linear or if the effect of intervention on anxiety scores is fully observed by week 4. Two-sided p-values ≤ 0.05 will be considered statistically significant. All analyses will be conducted using SAS/STAT version 9.4 (SAS Institute, Cary, NC).

Power and Sample size: Power and sample size will be computed via simulation. Normally distributed anxiety scores were assumed such that pre-intervention scores are distributed with mean of 18 (SD=4.0); post-intervention (at 12 weeks) distributed with a mean of 14 (SD=4.0) for a 20% reduction. Pre/post score correlation (ρ) was assumed to be 0.40. The final analysis set in each simulated data set consisted of n patients with baseline (score ≥ 16) and 12-week PSA anxiety score data, where n corresponds to the specified sample size per arm. **A total of n=48 patients will be recruited for the study, for a total of 24 in each study arm.**

Assuming an attrition rate of 25% (n=18 per treatment arm at 12 weeks for analysis), we will have >85% power at the 0.05 level of significance to detect a 20% reduction in PSA anxiety scores from baseline.

VIII ANTICIPATED RESULTS AND POTENTIAL PITFALLS

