We anticipate that our study will reveal important characteristics of patients with the diagnosis of prostate cancer, and test a CBT therapeutic approach to reducing the anxiety in these patients. We predict that an anxiety reduction in prostate cancer patients undergoing AHS will improve quality of life, delay radical, elective treatment, and potentially improve disease progression.

We have carefully designed our study so as to minimize the potential for pitfalls. For example, based on the current literature and our clinical experience, the chosen MAX-PC cutoff of 16 will identify a sufficient number of patients from our AHS cohort to enroll in group therapy. In an ongoing study, approximately 50% of our AHS patients exhibited a MAX-PC score of 16+. The risk of patient attrition due to lack of interest in the group-therapy intervention remains, but because we are fully implementing the group therapy into the AHS protocol, we anticipate that the attrition rate will be low, as this has been our experience in our ongoing AHS cohort.

We do not foresee any potential pitfalls that would alter or increase the risk level of the study subjects. The appropriate confidentiality safeguards are already implemented.

References Cited

¹Watts, S., Leydon, G., Eyles, C., Moore, C. M., Richardson, A., Birch, B., ... & Lewith, G. (2015). A quantitative analysis of the prevalence of clinical depression and anxiety in patients with prostate cancer undergoing active surveillance. *BMJ open*, 5(5), e006674.

²Tan, H. J., Marks, L. S., Hoyt, M. A., Kwan, L., Filson, C. P., Macairan, M., ... & Stanton, A. L. (2016). The Relationship between Intolerance of Uncertainty and Anxiety in Men on Active Surveillance for Prostate Cancer. *The Journal of urology*, 195(6), 1724-1730.

³Berg, C. J., Habibian, D. J., Katz, A. E., Kosinski, K. E., Corcoran, A. T., & Fontes, A. S. (2016). Active Holistic Surveillance: The Nutritional Aspect of Delayed Intervention in Prostate Cancer. *Journal of Nutrition and Metabolism*, 2016.

⁴van den Bergh, R. C., Korfage, I. J., & Bangma, C. H. (2012). Psychological aspects of active surveillance. *Current opinion in urology*, 22(3), 237-242.

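### Excluding therapy-arm men who miss more than 3 sessions, after randomisation, means the primary analysis no longer compares the randomised groups

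*Protocol*

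**What the plan says.** Section III (Study Design) has eligible men who "will be randomly assigned to the treatment or control group". On the therapy side, "Patients assigned to the treatment group will receive 12 weekly 1-hour sessions of structured group therapy intervention led by a licensed psychologist". On the other side, "Patients assigned to the control group will receive the standard AS educational material only".

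Section V, item 6 (Exclusion Criteria) lists conditions that can be checked at entry, then ends with a rule that cannot: "Participants in the treatment group who are absent from more than 3 therapy sessions will be excluded".

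Section III (Interventions) provides for missed assessments: "Those who are absent during the 4th week and/or 12th week will be given the questionnaires to fill out during the next session". The alternative it allows is a 7-day window.

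Section VII sets the primary analysis as ANCOVA, "regressing 12-week PSA anxiety scores onto baseline PSA scores and an indicator variable for treatment arm". The sample-size text adds "Assuming an attrition rate of 25% (n=18 per treatment arm at 12 weeks for analysis"). Section VIII concedes that "The risk of patient attrition due to lack of interest in the group-therapy intervention remains".

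The protocol has no statement that men are analysed as randomised.

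**The concern.** The attendance rule has three properties that together defeat the purpose of randomising. It acts after allocation. It depends on what a man does during treatment, which may well be related to his anxiety, the primary outcome. And it can remove men from one arm only.

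The ANCOVA adjusts for baseline score, but not for whatever else makes a man stop attending. If those men are more anxious at 12 weeks, or gain less from therapy, dropping them flatters the therapy arm. If they stop because they already feel better, dropping them penalises it. Lack of interest, the only reason for attrition that section VIII gives, fits either story.

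Section VII names the estimate, interval and significance of this treatment effect as the main results, so the study's headline finding is what is exposed.

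**Working it through.** **Step 1. Who can be excluded, and when.** More than 3 absences means at least 4 of 12 sessions. The earliest this can happen is session 4, for a man who has attended none; the latest is session 12. Controls cannot meet the condition. A man whose fourth absence falls in week 12 is owed a late questionnaire under section III and is excluded under section V, item 6. The protocol does not say which provision prevails.

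**Step 2. The plan's own figures.** Inputs from section VII: baseline mean 18, 12-week mean 14, SD 4.0, correlation 0.40, 24 per arm, 25% attrition, two-sided 0.05. Assumption: controls stay at 18.
- 24 × (1 − 0.25) = 18 per arm, as stated.
- Simulated ANCOVA power with 18 per arm is 87.9%, consistent with the stated figure of more than 85%.

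**Step 3. Bias from the rule when therapy has no effect.** Two inputs are not in the protocol and are assumed: k, the number of therapy men excluded out of 24, and r, the correlation between the tendency to be absent and the baseline-adjusted 12-week score (positive r: men doing worse miss sessions).
- Residual SD after baseline adjustment: 4.0 × √(1 − 0.40²) = 3.666.
- Bias = r × 3.666 × m, where m is the expected mean of the 24 − k lowest of 24 standard normal values: −0.287 for k = 4, −0.408 for k = 6, −0.527 for k = 8.
- Example, k = 6 and r = 0.3: 0.3 × 3.666 × (−0.408) = −0.45 points.

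Type I error comes from 200,000 simulated null trials per cell, with baseline scores truncated at 16, controls kept at 24 and two-sided 0.05. The simulated biases agree with the formula to within 0.01 point. Negative bias favours therapy.

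| Excluded of 24 | r = −0.3 | r = 0 | r = 0.2 | r = 0.3 | r = 0.5 |
|---|---|---|---|---|---|
| 4 | +0.32 / 6.0% | 0.00 / 5.0% | −0.21 / 5.4% | −0.32 / 6.1% | −0.53 / 7.9% |
| 6 | +0.45 / 6.8% | 0.00 / 4.9% | −0.30 / 5.8% | −0.45 / 6.8% | −0.75 / 10.2% |
| 8 | +0.58 / 7.7% | 0.00 / 4.9% | −0.39 / 6.2% | −0.58 / 7.7% | −0.97 / 12.9% |

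False wins for therapy have a nominal rate of 2.5%. With 6 excluded they are 5.7% at r = 0.3 and 1.0% at r = −0.3.

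**Step 4. If the 25% attrition already includes the exclusions.** Six men leave the therapy arm by the rule and six controls are lost at random, giving 18 per arm. The bias for r = 0.2 / 0.3 / 0.5 is unchanged at −0.30 / −0.45 / −0.75, with type I error 5.8% / 6.5% / 9.8%. Matching the numbers does not remove the bias.

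**Step 5. If therapy works but not for men who stop attending.** Suppose 18 men gain 4 points and 6 gain nothing (assumption), with absence otherwise unrelated to outcome. The effect of being assigned to therapy is (18 × 4 + 6 × 0) / 24 = 3.0 points. The analysis without absentees estimates 4.0, overstating it by 1.0.

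**The case against.** The strongest reply is that the rule says men are excluded without saying from what. It might mean only the therapy group, with follow-up and analysis untouched. The only analysis set described, in the sample-size text, is men with baseline and 12-week scores, with no attendance condition, and analysis sets are commonly left to the SAP, which was not available here. The ambiguity is real. But the paragraph begins by speaking of exclusion from the study and lists this rule with the rest. An SAP that kept these men would contradict the protocol, and it could not recover week 12 scores that were never collected.

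Second, the data would not be wholly silent. Only a man absent from all of the first four sessions could meet the rule by week 4, so most men excluded later would already have baseline and week 4 scores. That stands: those scores would hint at why men left. The week 12 outcome, on which the primary analysis rests, could still be missing.

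Third, the size is assumed, and the moderate cases are modest beside a standard error of about 1.1 points. Removing 8 men exceeds the plan's whole attrition allowance. Some men who stop attending would return no week 12 questionnaire in any case, so not all of the bias is due to the rule or curable by deleting it. All of this stands, and it limits what can be said about size.

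Fourth, this is a pilot of 48 men. It nonetheless states a primary hypothesis, a significance threshold and a power figure for this comparison.

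**Conclusion.** The concern holds. Followed as written, the protocol drops men from one arm only, after randomisation, for a reason that may be tied to the outcome, and no provision offsets this. That much rests on the text alone, reading exclusion as exclusion from the study, as its paragraph does.

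Neither the direction nor the size of the bias can be fixed from the protocol. If absence is unrelated to outcome and to benefit, there is none. Under moderate assumptions the distortion is noticeable but not large; under stronger ones the type I error is about double its nominal level. The more serious harm is that nobody could establish afterwards which case applied, because the week 12 scores of the excluded men need not exist. This must be corrected before follow-up, since uncollected outcomes cannot be recovered.

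**What to change.** Amend sections III, V and VII as follows.
- Delete the attendance sentence as a ground for exclusion from the study and from the analysis. Who continues to attend the therapy group is for the investigators to decide.
- Seek the week 4 and week 12 questionnaires from every randomised man whatever his attendance, unless he withdraws consent.
- Keep the primary ANCOVA, run on all randomised men with data in the arm to which they were assigned.
- Use the threshold of 3 or fewer absences only for a labelled per-protocol sensitivity analysis.
- Use the mixed model already planned as support for men without a week 12 score.
- State whether the 25% attrition counts men who stop attending, and revisit the power statement accordingly.

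The cost is a short amendment and questionnaire follow-up of men who stop attending. The expected effect may also be smaller. If a quarter of therapy men gain nothing and the rest gain 4 points (assumption), the effect is 3.0 points, with power of 74% at 24 analysed per arm and 61% at 18. If one in eight gain nothing, it is 3.5 points, with power of 87% and 76%. This is the cost of estimating the effect of assignment to therapy rather than the effect among men who kept attending.

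### The primary ANCOVA uses week-12 scores only, so men lost after week 4 add nothing to it, and dropout that differs by arm can bias it in either direction

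*Protocol*

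**What the plan says.** Section VII (Statistical methods) specifies the primary analysis as "regressing 12-week PSA anxiety scores onto baseline PSA scores and an indicator variable for treatment arm". Week 4 is not in that model. I read the PSA anxiety score of Section VII as the MAX-PC score, because the entry threshold of 16 attached to it is the MAX-PC threshold.

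Section VII (Power and Sample size) states "A total of n=48 patients will be recruited for the study, for a total of 24 in each study arm". It describes each simulated data set as holding "n patients with baseline (score ≥ 16) and 12-week PSA anxiety score data", and continues: "Assuming an attrition rate of 25% (n=18 per treatment arm at 12 weeks for analysis").

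Section VII plans week-4 summaries for each arm. Week 4 is modelled only in a secondary analysis, where "a mixed effects model will be used when the outcome vector consists of all three measurements"; its purpose is to examine the shape and timing of the response.

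Two other places bear on who is lost:
- Section VIII says "The risk of patient attrition due to lack of interest in the group-therapy intervention remains", although it expects attrition to be low.
- Section V, item 6, excludes therapy-arm men who miss more than 3 sessions. The control arm has no matching rule.

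**The concern.** A regression on the week-12 score can use only men who have one, unless missing scores are imputed, and the protocol shown names no imputation. On the planning figures, 24 − 18 = 6 men per arm would contribute nothing to the primary estimate, including those whose week-4 score is on file.

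This does harm when the relation between week-4 anxiety and dropout differs by arm. Two features make such a difference plausible: the attrition risk that the protocol names is tied to group therapy, which only one arm receives, and the attendance exclusion applies to that arm alone. The men left at week 12 could then be a differently selected group in each arm, and the comparison would lose part of the protection that randomisation gave it.

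**Working it through.** **1. The plan's own figure.** Inputs from Section VII: means 18 and 14, SD 4.0, pre/post correlation 0.40, 18 per arm analysed, two-sided 0.05. The control mean is assumed to stay at 18.
- Number analysed: 24 × (1 − 0.25) = 18 per arm.
- Unadjusted: SE = 4 × √(2/18) = 1.33; power = Φ(4/1.33 − 1.96) = Φ(1.04) = 0.851.
- With baseline adjustment: residual SD = 4 × √(1 − 0.4²) = 3.67; SE = 3.67 × √(2/18) = 1.22.
- Simulated ANCOVA (20,000 runs) gives power 0.875 with baseline truncated at 16 and 0.878 untruncated.

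The claim "we will have >85% power at the 0.05 level of significance to detect a 20% reduction in PSA anxiety scores from baseline" is reproduced for a 4-point effect.

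**2. Where bias arises.** Regress week 12 on baseline, arm and week 4, and let γ be the week-4 slope. The likelihood estimate of the week-12 effect is (arm coefficient) + γ × (week-4 arm difference in all men with week 4). The week-12 ANCOVA has the same form, but uses the week-4 arm difference in completers. Hence

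bias ≈ γ × (week-4 arm difference in completers − week-4 arm difference in all men).

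The bracket is zero if dropout is random. It is also zero if dropout selects on week 4 in the same way in both arms.

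For scale, let r be the week 4 to week 12 correlation and assume a baseline to week-4 correlation of 0.5 (not in the protocol). With equal SDs, γ = (r − 0.5 × 0.4)/(1 − 0.5²), which is 0.27, 0.53 and 0.80 for r = 0.4, 0.6 and 0.8. Each point by which the completers' week-4 difference is distorted carries over to week 12 by that fraction.

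**3. Simulated size.** 24 per arm, about 25% lost in each arm, control loss random, therapy-arm loss more likely with a higher week-4 score. The odds ratios and r are assumptions. Negative values favour therapy.

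| Therapy-arm dropout odds ratio per point | Bias of week-12 ANCOVA, r from 0.4 to 0.8 |
|---|---|
| 1.1 | −0.08 to −0.24 |
| 1.2 | −0.15 to −0.42 |
| 1.4 | −0.27, −0.51, −0.75 (r = 0.4, 0.6, 0.8) |
| 1.4, same in both arms | −0.02, 0.01, 0.00 |
| 1.4, direction reversed, r = 0.6 | +0.44 |

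A separate run gave about 0.1 to 0.7 points for odds ratios of 1.2 to 1.4. In the setting of the 1.4 row, the likelihood estimate using week 4 averaged −3.99, −4.00 and −4.00 against a true −4.0.

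Against the 4-point effect, 0.75/4 = 19%. Against a standard error of about 1.23, 0.75/1.23 = 0.6.

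**4. Type I error.** With therapy-arm loss driven by week-4 non-improvement (logistic slope 0.5 to 2 per SD, r = 0.6 to 0.8), the bias was 0.2 to 0.8 points and the error rate 5.3% to 10.3%.

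**5. Precision if dropout is random.** The variance ratio of ANCOVA to likelihood estimate was 1.01, 1.06 and 1.20 for r = 0.4, 0.6 and 0.8, a reduction of 1% (1 − 1/1.01) to 17% (1 − 1/1.20). Using week 4 costs no precision.

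**6. Limits of the repair.**
- If loss depends on the unseen week-12 score, bias only shrinks: from about −1.1 to between −0.5 and −0.9 in the strongest case run.
- If half the dropouts have no week-4 score, a bias of 0.12 to 0.27 remains. If none has one, nothing is gained.

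**The case against.** Several points on the other side stand.

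- A reader might infer that the protocol defines a completers-only analysis population. It does not: the words "n patients with baseline (score ≥ 16) and 12-week PSA anxiety score data" describe the simulated data sets. What is fixed is the outcome and covariates of the ANCOVA. The 18 per arm is a planning figure, and a SAP could still add imputation from week 4.
- A reader might infer that the analysis is valid only when dropout is unrelated to week-4 anxiety. That is too strong: the bias vanishes when both arms lose men in the same way.
- A reader might infer that the error will flatter therapy. The documents do not support a direction. Lack of interest is not lack of improvement; uninterested men may be the less anxious ones, and the sign then reverses.
- A reader might take the loss of a quarter of the men as established. Section VIII expects low attrition, and Section IV, item 10, calls withdrawal unlikely.
- Week-4 scores are not discarded from the trial, since the secondary model uses all three visits.
- An odds ratio of 1.4 per point is strong: over one SD of 4 points it is 1.4⁴ ≈ 3.8, in one arm only.

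These points narrow the claim. None makes the week-12-only ANCOVA the better primary analysis, because the alternative uses scores already collected, needs a weaker missing-data assumption and loses no precision.

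**Conclusion.** The point holds in conditional form. As stated, the primary model takes no information from a man who has a week-4 score but no week-12 score. Its estimate is biased if dropout depends on week-4 anxiety differently by arm. The protocol makes such a difference plausible but does not establish it.

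The size is about 0.1 to 0.75 points of a 4-point effect. This rests on 25% loss per arm, r of 0.4 to 0.8, and a dropout odds ratio of 1.2 to 1.4 per point in the therapy arm only; none of the last three is in the protocol. Even the upper end is about 0.6 of a standard error. This is a worthwhile, inexpensive improvement to a pilot, not a fatal flaw.

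**What to change.** Make the primary estimate the week-12 arm difference from a likelihood-based mixed model:
- Response: MAX-PC at weeks 4 and 12.
- Fixed effects: baseline MAX-PC, arm, week and arm-by-week.
- Unstructured covariance and Kenward-Roger degrees of freedom.
- Analysis set: all randomised men with at least one post-baseline score, in the arm assigned.

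State that missed sessions do not remove a therapy-arm man from the analysis, and reconcile Section V, item 6, with this. Still seek the week-12 questionnaire from men who stop therapy; this also serves men lost from therapy before week 4, whom the model cannot recover. Keep the week-12 ANCOVA as a sensitivity analysis, and add one for dropout that depends on unseen scores.

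Cost: no extra patients or visits, but some added follow-up effort. It is a re-specified model, not an exchange with the planned secondary one, which has baseline in the outcome vector and addresses the time course. The power statement should be re-run for it. The model assumes that dropout is explained by observed scores.
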